3.2.2. Pharmacokinetic Endpoints (Parts 1, 2 and 3)

For each study part, the serum concentration data for voriconazole and N-oxide voriconazole will be analysed using PKNCA (version 0.8.1 or higher) with R (version 3.2.2 or higher).

For Parts 2 and 3, sputum concentration of voriconazole will be analysed.

Pharmacokinetic parameters:

The following non-compartmental PK parameters of voriconazole and N-oxide voriconazole will be calculated:

Parts 1, 2 and 3 (in Part 3, Day 1 of TP1 and Day 1 of TP2): AUC_{0-t} , AUC_{0-inf} , AUC_{tau} , C_{max} , t_{max} , t_{max

AUC₀₋₁₂ for Part 1. AUC₀₋₂₄ for Part 2 and AUC₀₋₉₆ for Part 3.

AUC_{0--t}, AUC_{0-inf} and C_{max} for Part 3 will also be derived based on the Part 1 PK and separately the Part 2 PK time points, so that a like-for-like comparison between Part 3 and Part 1 and between Part 3 and Part 2 can be performed for these PK parameters.

Part 2 (Day 10): AUC_{0-tau}, C_{max,ss}, t_{max,ss}, C_{min}, C_{trough}, C_{ss,av}, %fluctuation and %swing (as appropriate and when applicable). PK parameters will be derived in addition to those detailed for Day 1.

Accumulation ratios will be calculated from Day 1 and Day 10 AUC_{0-tau} and C_{max} values, and the linearity ratios will be calculated from the ratio of the Day 10 AUC_{tau} and Day 1 AUC_{0-inf}.

Metabolite ratios (as appropriate) will be calculated for AUC and C_{max} parameters. Additional PK parameters may be calculated if deemed appropriate.

4. Study Design

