9.4.4.2. Bioavailability

The PK endpoints estimated from Part 3 will be analysed to assess relative bioavailability of Test to Reference by fitting a mixed effects ANOVA model to the loge transformed PK parameter including fixed effect terms for treatment, period, sequence and sex and a random effect term for subject (nested within sequence). The adjusted geometric mean ratio (GMR) (Test: Reference) and the corresponding 90% confidence interval (CI) for the adjusted GMR will be presented.

In addition, the PK endpoints will be compared between asthma subjects in Part 3 and healthy subjects in Part 1 and separately with asthma subjects in Part 2 to assess relative bioavailability of the ZP-059 dose taken in Part 3 in these populations. An ANOVA model will be fitted to the loge transformed PK parameter including terms for the population group (i.e., healthy subjects or asthma subjects) and sex. The adjusted GMR and 90% CI for the adjusted GMR for the comparison between the two populations for the relevant dose will be provided, where the ratio is defined as either Part 3 subjects/Part 1 subjects or Part 3/Part 2 subjects, depending on the comparison.

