#### 7.12.3 Dose proportionality

Dose proportionality of ZP-059 will be assessed by fitting a power model as follows:

$$log_{10}(y) = \alpha + \beta \ log_{10}(dose)$$

Where  $\alpha$  represents the random subject effects for intercept and dose. A value of 1 for  $\beta$  indicates perfect dose proportionality. Therefore, the estimate of  $\beta$  together with the corresponding 90% confidence interval (CI) will be used to quantify dose proportionality. The increase in concentration over the dose range will be estimated by the ratio of the expected concentration with the highest dose to that of the lowest dose. This will be derived by back-transforming the difference on the log10 scale between the two doses and will be accompanied by its associated 90% confidence interval. If the exposure is dose proportional there should be a fold increase equal to the ratio of highest: lowest dose across the dose range.

If it isn't possible to fit random subject slopes a common fixed effect slope will be fitted.

Dose proportionality will be assessed for each of the following PK endpoints for voriconazole and n-oxide voriconazole separately:

- Cmax
- AUC0-t, where t is 12 hours for Part 1, 24 hours for Part 2 and 96 hours for Part 3.
- AUC0-inf

These will be performed separately for Part 1 and Part 2 at Day 1 and Day 10. This analysis will be performed if 3 or more dose levels are used for the Part.

Dose proportionality will also be assessed using an analysis of variance (ANOVA) method. A mixed effects model will be fitted with fixed effects for dose and random effects for subject. The difference between the dose levels will be presented along with a 90% confidence interval and p-value.

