#### 7.12.4 Bioavailability

The PK endpoints (see Section 7.12.3) estimated from Part 3 of the study will be analysed to assess relative bioavailability of Inhaled Voriconazole (ZP-059) to Oral Voriconazole (VFEND®) by fitting a mixed effects analysis of variance (ANOVA) model to the loge transformed PK parameter including fixed effect terms for treatment, period, sequence and sex and a random effect term for subject (nested within sequence). The adjusted geometric mean ratio (GMR) (Inhaled: Oral) and the corresponding 90% confidence interval (CI) for the adjusted GMR will be presented.

In addition, the PK endpoints will be compared between asthma subjects in Part 3 and healthy subjects in Part 1 and separately with asthma subjects in Part 2 to assess relative bioavailability of the Inhaled Voriconazole (ZP-059) dose taken in Part 3 in these populations. An ANOVA model will be fitted to the loge transformed PK

parameter including terms for the population group (i.e., healthy subjects or asthma subjects) and sex. The adjusted GMR and 90% CI for the adjusted GMR for the comparison between the two populations for the relevant dose will be provided, where the ratio is defined as either Part 3 subjects/Part 1 subjects or Part 3/Part 2 subjects, depending on the comparison.

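### The Part 3 versus Part 2 PK comparison is written with a group factor that has only one level in those data, and neither the Part 2 day nor the AUC interval is fixed

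*SAP*

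**What the plan says.** SAP 7.12.4 plans a comparison of Part 3 with the healthy subjects of Part 1 and "separately with asthma subjects in Part 2 to assess relative bioavailability" of the ZP-059 dose used in Part 3. One model serves both: an ANOVA on the log-transformed "parameter including terms for the population group (i.e., healthy subjects or asthma subjects) and sex". Protocol 9.4.4.2 has the same term: "including terms for the population group (i.e., healthy subjects or asthma subjects) and sex". The planned output is "The adjusted GMR and 90% CI for the adjusted GMR for the comparison between the two populations", "where the ratio is defined as either Part 3 subjects/Part 1 subjects or Part 3/Part 2 subjects, depending on the comparison".

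The endpoints come by cross-reference from SAP 7.12.3: Cmax, AUC0-t (t nominally 12, 24 and 96 h for Parts 1, 2 and 3) and AUC0-inf. Of the dose-proportionality analyses, that section says: "These will be performed separately for Part 1 and Part 2 at Day 1 and Day 10". SAP 7.12.4 does not say which Part 2 day is set against the single Part 3 dose.

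Protocol 3.2.2 re-derives the Part 3 parameters on the Part 1 and Part 2 time points "so that a like-for-like comparison between Part 3 and Part 1 and between Part 3 and Part 2 can be performed". It names no day there, and the SAP does not restate the provision. For Part 2 Day 10, protocol 3.2.2 gives a further list and adds that "PK parameters will be derived in addition to those detailed for Day 1".

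Part 2 dosing may be once daily (QD) or twice daily (BID) in any cohort (protocol 4.1.2).

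**The concern.** Two details that determine the Part 3/Part 2 ratio are not settled by the text.

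- **The factor.** The parenthesis defines the group term as healthy or asthma. That suits Part 3 against Part 1. Against Part 2, every subject has asthma and the term cannot separate the groups.
- **The data.** Part 3 gives a single dose. Part 2 offers a single-dose profile (Day 1) and a profile after repeated dosing (Day 10). If Day 10 entered, accumulation would appear in the ratio as a difference in relative bioavailability between mild and mild-to-moderate asthma. If Part 2 were BID, AUC0-24 on Day 1 would span two administrations against one in Part 3.

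The study is open-label. A choice left open in the SAP can be made after the concentrations are known.

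**Working it through.** The plan states no figure for this comparison, so there is nothing to reproduce. There are two checks.

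**1. Is the contrast in the model?** Inputs: 16 Part 3 subjects (protocol 9.2) and 6 in the Part 2 or Part 1 cohort at the same dose (protocol 4.1), with sex balanced as protocol 4.1 intends. The design columns are intercept, group and sex.

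| Comparison | Group coding | Rank (of 3) |
|---|---|---|
| Part 3 v Part 1 | healthy/asthma | 3 |
| Part 3 v Part 2 | healthy/asthma | 2 |
| Part 3 v Part 2 | study part | 3 |

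Coded literally, the group column equals the intercept in the second row, and no group effect is estimable. With study part, residual df = 22 − 3 = 19. The 90% CI is the GMR divided and multiplied by exp(t × s × √(1/16 + 1/6)), with t = 1.729 and s = √ln(1 + CV²). For assumed between-subject CVs of 30%, 50% and 80% that factor is about 1.28, 1.48 and 1.79.

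**2. What does the choice of day do?** Assumptions: one compartment, linear kinetics, instant input, equal dose and equal true bioavailability. The half-life h is also assumed. Let x = 2^(−12/h). In units of C0/k, where C0 is the initial concentration and k = ln2/h:

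- Part 3 single dose, AUC0-24: 1 − x²
- Part 2 QD, Day 1: 1 − x², so the ratio is 1
- Part 2 QD, Day 10 (near steady state): 1, so the ratio is 1 − x²
- Part 2 BID, Day 1: (1 − x²) + (1 − x), so the ratio is (1 + x)/(2 + x)
- Part 2 BID, Day 10 (morning dose plus residue of 18 earlier doses): 1 + x, so the ratio is 1 − x

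For h = 6 h, x = 0.25. QD Day 10 is 1 − 0.0625 = 0.94, BID Day 1 is 1.25/2.25 = 0.56, and BID Day 10 is 0.75.

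| Assumed half-life | QD Day 1 | QD Day 10 | BID Day 1 | BID Day 10 |
|---|---|---|---|---|
| 3 h | 1.00 | 1.00 | 0.52 | 0.94 |
| 6 h | 1.00 | 0.94 | 0.56 | 0.75 |
| 9 h | 1.00 | 0.84 | 0.58 | 0.60 |
| 12 h | 1.00 | 0.75 | 0.60 | 0.50 |

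These are ratios of true areas. One qualification applies to BID Day 1. The Part 2 schedule (protocol 1.2.2, notes u and v) samples at 1.5, 2, 3, 4, 12 and 24 h, with the 12 h sample taken before the evening dose. Nothing is drawn between 12 and 24 h, so a trapezoid would largely miss the evening peak. Take h = 6 h and C0 = 1, with the pre-dose value zero. The linear trapezoid over 0–12 h is 5.98 in both parts. Over 12–24 h it is 6 × (0.25 + 0.0625) = 1.875 for a single dose and 6 × (0.25 + 0.3125) = 3.375 for BID. The reported ratio would be 7.85/9.35 = 0.84. The same calculation gives 0.92 at 3 h and 0.81 at 12 h. The ratio is still not like-for-like, and it depends on what the sampling misses.

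Over 0–12 h on Day 1, both parts contain one dose, so the expected ratio is 1.00 under BID. Over 0–24 h on Day 1 it is 1.00 under QD.

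**The case against.** A reader might infer that the planned GMR cannot be produced at all. The documents do not support that. The sentence after the model defines the ratio by study part, and Parts 2 and 3 are distinct populations (mild, and mild to moderate, asthma). A competent programmer would probably code study part and obtain the GMR. The rank result shows only what literal coding would do. Nor does the missing day affect whether the model can be fitted; it affects which data enter.

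A reader might also infer that Day 10 is planned. It is not stated. The synopsis introduces AUC0-t, AUC0-inf and Cmax as single-dose parameters. Protocol 3.2.2 treats the Day 10 list as additional, and SAP 3.2.2 gives Day 10 its own labels (AUCtau, Cmax,ss). The sentence in SAP 7.12.3 naming both days schedules dose proportionality, while 7.12.4 cites that section for its endpoints. SAP 3.2.2 also reports accumulation separately as a Day 10 to Day 1 ratio.

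Finally, the comparison is descriptive, is not a stated Part 3 objective, and arises only if a Part 2 cohort receives the Part 3 dose.

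All of that stands, and it limits the severity. It does not remove the mis-stated term, and it leaves Day 1 as an inference. Nor does Day 1 alone settle the BID case. SAP 3.2.2 notes that t may vary with the regimen but does not say how the two parts are then matched.

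**Conclusion.** The point holds as a specification defect of minor to moderate severity. The group term is wrong for Part 3 versus Part 2, and the text needed to fix the estimand (day and AUC interval) is missing from SAP 7.12.4. The day and interval matter more than the factor, because common-sense coding cannot resolve them.

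The size depends on assumptions the documents do not supply, namely half-life and linear kinetics. If Day 10 were used, the effect is negligible for QD with a 3 h half-life and reaches a ratio of 0.50 for BID with a 12 h half-life. If Day 1 AUC0-24 were used under BID, the true-area ratio is about 0.52 to 0.60 for half-lives of 3 to 12 h, and about 0.81 to 0.92 as the scheduled samples would measure it. Under QD on Day 1 there is no distortion.

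No sample size, error rate, primary safety result or inhaled-to-oral GMR is affected.

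**What to change.** In SAP 7.12.4:

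- For Part 3/Part 2, fit study part and sex. Keep healthy/asthma and sex for Part 3/Part 1.
- State that only Part 2 Day 1 parameters, from subjects at the Part 3 dose, enter the comparison.
- State that AUC is compared over the same single-dose interval in both parts: 0–24 h if the Part 2 cohort is QD, and 0–12 h if it is BID, ending at the existing 12 h sample before the evening dose.
- Restate the protocol 3.2.2 provision, so that Part 3 is derived on the matching Part 2 time points.

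Protocol 9.4.4.2 has the same factor wording. The change can be recorded in SAP Section 2, which lists departures from the protocol analysis. The cost is a few sentences and a small change to the analysis code. The samples are already scheduled in both parts, so no new data are needed.

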## 7.13 SAFETY EVALUATION

The safety and tolerability of ZP-059 will be assessed based on AEs, clinical laboratory assessments, vital signs, ECGs, pulmonary function and pulse oximetry parameters.

Details regarding the evaluation of these data are given in the following respective sections.

#### 7.13.1 Adverse Events

AEs will be coded using the latest MedDRA dictionary version. The version used will be indicated in the data summaries and listings.

#### 7.13.1.1 Treatment-emergent Adverse Events

A treatment-emergent adverse event (TEAE) is defined as an AE that started on or after the start of the administration of study treatment. If adverse event dates are incomplete and it is not clear whether the adverse event was treatment-emergent, it will be assumed to be treatment-emergent.

In Part 3 of the study, AEs are treatment emergent and accountable to the Period 1 treatment if they started on or after the start of the administration of study treatment in Period 1 up to the first administration of study treatment in Period 2. For Period 2, AEs are treatment emergent and accountable to the Period 2 treatment if they started on or after the start of the administration of study treatment in Period 2 up to the end of the follow-up period.

A treatment related TEAE is defined as a TEAE that is related to the study treatment. If the TEAE has a missing relationship it is assumed to be related to the study treatment for analysis purposes.

A summary table will present the following:

- TEAEs (events and subjects).
- Serious TEAEs (events and subjects).
- Serious study treatment related TEAEs (events and subjects).
- TEAEs by severity (mild/moderate/severe) (events and subjects).
- TEAEs by relationship to study treatment (events and subjects).
- TEAEs leading to withdrawal from study (subjects only).
- TEAEs leading to discontinuation of study treatment (subjects only).
- Study treatment related TEAEs leading to discontinuation of study treatment (subjects only).
- TEAEs leading to death (subjects only).

In the above summaries, if a subject experienced more than one TEAE, the subject will be counted once using the most related event for the "by relationship to study

treatment" and "related to study treatment" summaries, and by the worst severity for the "by severity" summary.

The following tables will be presented:

- TEAEs by SOC and PT.
  - If a subject experienced more than one TEAE assigned to the same treatment, the subject will be counted once for each SOC and once for each PT within that treatment.
- TEAEs by PT.
  - If a subject experienced more than one TEAE assigned to the same treatment, the subject will be counted once for each PT within that treatment.
- TEAEs by SOC, PT and severity.
  - If a subject experienced more than one TEAE assigned to the same treatment, the subject will be counted once for each SOC and once for each PT at the worst severity/CTC grade within that treatment.
- TEAEs by SOC, PT and relationship to study treatment and the related categories (related/unrelated).
  - If a subject experienced more than one TEAE assigned to the same treatment, the subject will be counted once for each SOC and once for each PT using the most related event within that treatment.

For all of the above, SOC and PT will be presented in decreasing frequency of the total number of subjects with TEAEs.

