8.12.1. Time Period and Frequency for Collecting AE and SAE Information

All AEs and SAEs will be collected from the signing of the informed consent form (ICF) until the follow-up phone call (Section 1.2).

All SAEs will be recorded and reported to the sponsor's Drug Safety Unit and Medical Monitor immediately and under no circumstance should this exceed 24 hours, as indicated in Appendix 3. The investigator will submit any updated SAE data to the sponsor within 24 hours of it being available.

Investigators are not obligated to actively seek AEs or SAEs after conclusion of the study participation. However, if the investigator learns of any SAE, including a death, at any time after a subject has been discharged from the study, and he/she considers the event to be reasonably related to the study IMP/s or study participation, the investigator must promptly notify the sponsor.

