10.3.1. Definition of AE

AE Definition

- An AE is any untoward medical occurrence in a patient or clinical study subject, temporally associated with the use of IMP, whether or not considered related to the study IMP.
- NOTE: An AE can therefore be any unfavorable and unintended sign (including an abnormal laboratory finding), symptom, or disease (new or exacerbated) temporally associated with the use of study intervention.

Events Meeting the AE Definition

- Any abnormal laboratory test results (hematology, clinical chemistry, or urinalysis) or other safety assessments (e.g., ECG, radiological scans, vital signs measurements), including those that worsen from baseline, considered clinically significant in the medical and scientific judgment of the investigator (i.e., not related to progression of underlying disease).
- Exacerbation of a chronic or intermittent pre-existing condition including either an increase in frequency and/or intensity of the condition.
- New conditions detected or diagnosed after IMP administration even though it may have been present before the start of the study.
- Signs, symptoms, or the clinical seguelae of a suspected drug-drug interaction.
- Signs, symptoms, or the clinical sequelae of a suspected overdose of either study intervention or a concomitant medication. Overdose per se will not be reported as an AE/SAE unless it is an intentional overdose taken with possible suicidal/self-harming intent. Such overdoses should be reported regardless of sequelae.

Events NOT Meeting the AE Definition

- Any clinically significant abnormal laboratory findings or other abnormal safety assessments which are associated with the underlying disease, unless judged by the investigator to be more severe than expected for the subject's condition.
- The disease/disorder being studied or expected progression, signs, or symptoms of the disease/disorder being studied, unless more severe than expected for the subject's condition.

- Medical or surgical procedure (e.g., endoscopy, appendectomy): the condition that leads to the procedure is the AE.
- Situations in which an untoward medical occurrence did not occur (social and/or convenience admission to a hospital).
- Anticipated day-to-day fluctuations of pre-existing disease(s) or condition(s) present or detected at the start of the study that do not worsen.

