- The investigator will use clinical judgment to determine the relationship.
- Alternative causes, such as underlying disease(s), concomitant therapy, and other risk factors, as well as the temporal relationship of the event to study intervention administration will be considered and investigated.
- The investigator will also consult the Investigator's Brochure (IB) and/or Product Information, for marketed products, in his/her assessment.
- For each AE/SAE, the investigator **must** document in the medical notes that he/she has reviewed the AE/SAE and has provided an assessment of causality.
- There may be situations in which an SAE has occurred and the investigator has
 minimal information to include in the initial report to the Sponsor. However, it is
 very important that the investigator always make an assessment of causality for
 every event before the initial transmission of the SAE data to the Sponsor.
- The investigator may change his/her opinion of causality in light of follow-up information and send a SAE follow-up report with the updated causality assessment.
- The causality assessment is one of the criteria used when determining regulatory reporting requirements.

Follow-up of AEs and SAEs

- The investigator is obligated to perform or arrange for the conduct of supplemental measurements and/or evaluations as medically indicated or as requested by the Sponsor to elucidate the nature and/or causality of the AE or SAE as fully as possible. This may include additional laboratory tests or investigations, histopathological examinations, or consultation with other health care professionals.
- If a subject dies during participation in the study or during a recognised followup period, the investigator will provide the Sponsor with a copy of any post-mortem findings including histopathology.
- New or updated information will be recorded in the originally completed CRF.
- The investigator will submit any updated SAE data to the Sponsor within 24 hours of receipt of the information.

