#### 7.13.1.2 Adverse Events of Special Interest

An adverse event of special interest (AESI) is an AE of scientific and medical interest and is defined as an AE that started on or after the start of administration of study treatment to the end of the safety follow up period.

The following AESIs will be monitored during the study.

- Respiratory Events:
  - Moderate or severe dyspnoea/wheeze
  - Moderate or severe cough
  - o Moderate or severe bronchospasm
- Moderate or severe visual impairment/hallucination
- Anaphylaxis and severe allergic reaction
- Hepatotoxicity ≥3X Upper Normal Limit (ULN) for Aspartate Aminotransferase (AST), Alanine Aminotransferase (ALT) and bilirubin
- COVID-19

If necessary, a summary table will present the following

- AESI (events and subjects).
- Non-serious AESIs (events and subjects).

- Serious AESIs (events and subjects).
- Serious study treatment related AESIs (events and subjects).
- AESIs by severity (mild/moderate/severe) (events and subjects).
- AESIs by relationship to study treatment (events and subjects).
- AESIs leading to withdrawal from study (subjects only).
- AESI leading to discontinuation of study treatment (subjects only).
- Study treatment related AESIs leading to discontinuation of study treatment (subjects only).
- AESIs leading to death (subjects only).

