#### 7.13.1.3 Adverse Event Listings

Adverse event data will be listed in full and will include a treatment emergent flag, a special interest flag, the time of onset and cessation of event relative to first dosing of study treatment and duration of AE.

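### TEAE status, Part 3 treatment attribution and AESI status rest on onset date alone, so an AE already open at a dose that worsens after it can be left out of the summary tables or graded under the wrong drug

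*SAP*

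**What the plan says.** **TEAE definition (SAP 7.13.1.1).** "A treatment-emergent adverse event (TEAE) is defined as an AE that started on or after the start of the administration of study treatment". Protocol 9.4.3 gives no definition of its own and leaves the detail to the SAP.

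**Part 3 attribution (SAP 7.13.1.1).** AEs are "accountable to the Period 1 treatment if they started on or after the start of the administration of study treatment in Period 1" and before the Period 2 dose. The Period 2 rule has the same form.

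**Severity table (SAP 7.13.1.1).** A subject with several events is "counted once for each SOC and once for each PT at the worst severity/CTC grade within that treatment".

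**AESIs (SAP 7.13.1.2).** An AESI is "defined as an AE that started on or after the start of administration of study treatment". Protocol 8.12.7 likewise limits AESIs to onset after dosing.

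**Collection (Protocol 8.12.1).** "All AEs and SAEs will be collected from the signing of the informed consent form (ICF) until the follow-up phone call". Screening may be up to 28 days before dosing (Protocol 8.1).

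**Updates (Protocol 10.3.3).** "New or updated information will be recorded in the originally completed CRF".

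**What counts as an AE (Protocol 10.3.1).** The list includes "Exacerbation of a chronic or intermittent pre-existing condition including either an increase in frequency and/or intensity of the condition".

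**Listing (SAP 7.13.1.3).** Every AE is listed with a treatment-emergent flag and a special-interest flag, plus "the time of onset and cessation of event relative to first dosing of study treatment and duration of AE".

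**The concern.** Safety and tolerability is the primary endpoint of every part (SAP 3.2.1) and no hypothesis is tested, so the descriptive AE tables are the primary result. An onset-only rule has no place for an AE that was already open when a dose was given and then got worse.

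The overview lines for serious, related and discontinuation-causing events are all subsets of TEAEs, so an event that fails the onset test is missing from all of them.

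AESIs show the gap most clearly. Cough, dyspnoea/wheeze, bronchospasm and visual impairment qualify only at moderate or severe grade. A rise from mild to moderate after dosing is what makes the event an AESI, yet the onset rule shuts it out if the mild phase began before dosing.

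In Part 3 the two doses may be as little as 96 hours apart, and the 96-hour Period 1 procedures can serve as the Period 2 pre-dose assessments (Protocol 1.2.3.2). An event from Period 1 can therefore still be open at the Period 2 dose. SAP 7.9 foresees this for concomitant medication, which is reported under both periods when it carries over. There is no equivalent for AEs.

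**Working it through.** The documents give no figure on this point, so the check is mainly of the text.

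**1. Can an AE be open at a dose?** Yes. Collection starts at consent, up to 28 days before the first dose, and Part 3 has a second dose at least 96 hours after the first.

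**2. Does a rise in intensity create a new onset date?** The documents do not say. Protocol 10.3.3 points to the existing CRF for updates but does not mention changes in intensity. Protocol 10.3.1 makes worsening of a pre-existing condition an AE, but does not say how to record worsening of an AE already entered. The rest of the check assumes one record, keeping its start date and carrying its worst grade.

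**3. Error 1: onset between consent and first dose, worsening after dosing.** The start date precedes dosing, so the event is neither a TEAE nor an AESI. It is absent from the summaries and present in the listing, where the treatment-emergent flag follows the same rule.

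**4. Error 2: Part 3, oral voriconazole first, event mild in Period 1 and severe after ZP-059 in Period 2.** For one such subject among 16:

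| | Oral voriconazole column | ZP-059 column |
|---|---|---|
| SAP rule | 1/16, severe | 0/16 |
| Assigned by period of worsening | 1/16, mild | 1/16, severe |

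Oral incidence at any grade is 1/16 either way; only its grade is wrong. ZP-059 is short of one event, 1/16 = 6.25%. In the ZP-059-first sequence the columns swap: ZP-059 carries a grade reached after the oral dose, and the oral column is one event short.

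**5. Size per subject.**
- Part 1 or 2 cohort of 6: 1/6 = 16.7%.
- Part 3: 1/16 = 6.25%, plus one misplaced grade for error 2.

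**6. How likely is at least one such event?** The documents give no rate. Suppose each subject independently has a chance p of an AE open at the relevant dose, kept as one record, that then worsens. P(at least one among n) = 1 − (1 − p)^n. Allocation is 1:1 (SAP section 5), so about 8 of 16 take oral voriconazole first.

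| Assumed p | Part 1 or 2 cohort, n = 6 | Part 3 oral-first, n = 8 |
|---|---|---|
| 2% | 0.114 | 0.149 |
| 5% | 0.265 | 0.337 |
| 10% | 0.469 | 0.570 |
| 20% | 0.738 | 0.832 |

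For example, at p = 5% and n = 8: 1 − 0.95^8 = 0.337. The range shows scale only and is not an estimate.

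**The case against.** **The recording premise is inferred.** The sentence in Protocol 10.3.3 is a general follow-up instruction that names the CRF, not the AE line or its start date. If the site opens a new entry when intensity rises, both errors disappear. This stands, and it makes the finding conditional. It does not remove it, because no text requires a new entry.

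**Most worsening is already covered.** A reader might infer that the plan loses worsening events in general, including asthmatic cough and wheeze. The documents do not support that. Exacerbation of a pre-existing condition is an AE in its own right, and if entered with a post-dose onset it is a TEAE. Part 2 events that start after the first dose and worsen on later doses are also TEAEs already. Nor can an AE caused by screening sputum induction arise outside Part 3: Part 1 has no induction, and Part 2 samples sputum on Day 7.

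**Nothing is deleted, and dose decisions do not depend on it.** All AEs are listed. The escalation and stopping rules (Protocol 6.6.4 and 6.6.5) refer to SAEs and severe AEs related to IMP, not to the TEAE flag. Spirometry is summarised separately as change from baseline. All of this stands; the effect is on the summary tables.

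**Onset timing in the listing is minor.** Timing from the first dose would show a Part 3 event just after the Period 2 dose at about 96 hours or more. But a within-period reading is possible, and period, period day and dosing times are also listed (SAP 7.2.2 and 7.10), so time since dose can be derived.

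**Conclusion.** The concern holds for a limited set: AEs already open at a dose, kept as one record, that worsen after it. For these the stated rules give a wrong summary of the primary endpoint. An AE from before the first dose is left out of the TEAE and AESI tables; a Part 3 event from Period 1 is graded under the wrong drug and missing under the right one.

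The number of such events is unknown. Each affected subject is 16.7% of a six-subject cohort; in Part 3 each is 6.25% of the 16, with a misplaced grade as well when the event began in Period 1. These sizes assume that the subject has no other TEAE counted in the same row and, for the grade, that the single record carries the worst severity.

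Two further inferences are tempting and not supported. The first is that the rule systematically flatters ZP-059: the error runs in either direction, depending on sequence. The second is that 6.25 points of incidence move from one treatment column to the other: the Period 1 event did occur and stays in its column, so only its grade is misplaced. Should-fix.

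**What to change.** 1. **TEAE definition (SAP 7.13.1.1).** Define a TEAE as an AE that starts, or increases in severity, on or after the start of dosing.
2. **Part 3 attribution.** Count a worsening on or after the Period 2 dose under the Period 2 treatment at the worsened grade. Keep the earlier grade under the Period 1 treatment.
3. **Recording.** Tell the site, in the eCRF completion instructions, to open a new record or enter a dated severity change when severity increases. Without that date, steps 1 and 2 cannot be programmed.
4. **AESIs.** Make the same change in SAP 7.13.1.2 and in Protocol 8.12.7 together, since both now rest on onset; changing the SAP alone would create a mismatch.
5. **Optional.** In Part 3, list AE onset relative to the dose of the assigned period.

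The cost is a few sentences in the SAP, one eCRF instruction, a small programming change and a matching protocol wording change for AESIs. It should be done before database lock; AE records already entered without a dated severity change would need checking against source.
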